#### **11.4.3.2 Laboratory data and vital signs**

The summary statistics (including mean, median, Q1, Q3, standard error, minimum and maximum) of all laboratory variables, all vital signs parameters (raw data and changes from baseline) will be calculated for each visit, last and worst value assessed during the treatment period and presented by treatment group. For selected parameters, mean changes from baseline with the corresponding standard error will be plotted over time (at same time points) in each treatment group.

The incidence of PCSAs at any time during the TEAE period will be summarized by treatment group whatever the baseline level and/or according to the following baseline categories:

- Normal/missing;
- Abnormal according to PCSA criterion or criteria.

For laboratory parameters for which PCSA criterion is not defined, similar table(s) using the normal range could be provided.

### Hepatitis C antibody:

The number and percentage of patients with an observed seroconversion for Hepatitis C Test will be provided by treatment group.

#### **11.4.4 Other endpoints:**

##### **11.4.4.1 Cardiovascular events of interest (other than efficacy endpoints)**

Clinically significant complications or procedures (not planned at the time of randomization) related to peripheral arterial disease, and venous thromboembolic events (see [Section 9.3.7](#)) will be analyzed using a time-to-event approach (Kaplan-Meier methodology) in the ITT population. Time from randomization to the first occurrence of the event will be calculated. Patients without any event will be censored using the same methodology as for the primary efficacy endpoint.

#### **11.4.4.2 Other endpoints**

All analyses for other endpoints (not already described above) will be performed on the Safety population. The baseline value is defined as the last available value before first double-blind IMP injection.

The number and percentage of patients with calculated LDL-C <25 mg/dL (respectively, LDL-C <15 mg/dL) will be provided by treatment group and visit.

Exploratory variables defined in [Section 9.3](#) will be summarized by time points using number of available data, mean, SD, median, minimum, and maximum for each treatment group (for hs-CRP, Q1 and Q3 will be also provided). The time profile of each parameter will be also plotted by treatment group with the corresponding standard errors. For hs-CRP, the incidence of PCSA at any time during the TEAE period will be also summarized by treatment group using descriptive statistics.

The anti-alirocumab antibody status (positive/negative) and antibody titers will be summarized by treatment group and visit using descriptive statistics. Anti- alirocumab antibody will be further described in terms of time-to-onset, persistence (transient/persistent anti- alirocumab antibodies). Correlations between antibody titers, safety and/or efficacy endpoints could be also provided by graphical methods. Further details will be provided in SAP.

#### **11.5 INTERIM ANALYSIS**

Two interim analyses (IA) are planned, when 50% and 75% of the total number of expected events have occurred:

- Interim analysis for futility will be conducted, when approximately 807 events (50% of the targeted number of primary endpoint events) have occurred.
- Interim analysis for futility and overwhelming efficacy will be conducted, when approximately 1210 events (75% of the targeted number of primary endpoint events) have occurred.

Both IA will be performed by the external independent CV DMC Statistician and will be reviewed under the supervision of the CV DMC. The CV DMC will also review secondary efficacy endpoints and safety data (AEs, laboratory data, vital signs) available at the time of the IA.

Control of the type I and type II error will be ensured using gamma (-5) spending function for Type II error (futility) and Gamma (-22) for Type I error (efficacy) at each IA (the Type I error spending function is also applied at the first IA, even if the objective of this first IA is only futility). It has to be noted that, in order to protect the global type one error in case the decision is taken to overrule the futility rule, non binding boundaries were used.

The following table shows the stopping rules at each interim analysis (using the sample size assumptions described in [Section 11.1](#)):

**Table 4 - Interim Analyses stopping boundaries corresponding to Gamma (-22) type I error and Gamma (-5) type II error spending functions**

Timing of analyses	Stopping boundaries (one-sided p-value and Hazard ratio)	
	Futility	Overwhelming efficacy
First IA : 50% of targeted events	p > 0.548 (⇔ HR > 1.008)	NA
Second IA: 75% of targeted events	p > 0.19 (⇔ HR > 0.951)	p < 0.0001* (⇔ HR < 0.802)

Calculations done using EAST 5.4

\*Should the second interim analysis be triggered just before or after 1210 events have been reached, the exact nominal significance level to be used at the second IA would be re-computed based on a Gamma(-22) spending function.

The CV DMC could consider early stopping of the study for overwhelming efficacy at the second IA, if the following conditions are met:

- Stopping boundaries for overwhelming efficacy are crossed
- Positive trend observed for secondary efficacy endpoints, including all cause mortality, and no excess of non-CV mortality
- Consistency of the treatment effect on the primary efficacy endpoint across subgroups and regions

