
STATISTICAL CONSIDERATIONS
	
Sample size determination:                  Based on the targeted population for the study, a Kaplan-Meier event rate in placebo group of 11.4% at 48 months (3.8% at 12 months, 6.4% at 24 months, 9.0% at 36 months) is assumed. With a 40-month recruitment period, a 64-month total study duration, 9300 patients per group (total 18,600), and 1,613 patients experiencing at least one primary endpoint event, the study has 90% power (one-sided Logrank test at the overall 0.025 alpha level) assuming a 15% risk reduction associated with alirocumab treatment. The sample size calculation takes into account two interim analyses.
 
Analysis Populations:                  Randomized population includes any patients who have been allocated to a randomized treatment regardless of whether the treatment kit was used or not. Efficacy analyses will be performed on the intention-to-treat (ITT) population, consisting of all randomized patients. Patients in the ITT population will be analyzed according to the treatment group allocated by randomization.
 
The safety population consists of the randomized population who actually received at least one dose or partial dose of IMP analyzed according to the treatment actually received.
 
Primary Analysis:                  The primary endpoint will be compared between treatment groups by a log-rank test, stratified by region (North America, South America, Western Europe, Eastern Europe, Asia, other region). The distribution will be estimated by treatment group with Kaplan-Meier methodology. Treatment hazard ratios (HRs) for the primary endpoint will be estimated from Cox regression models stratified by region.
 
Analysis of the main secondary endpoints                  A hierarchical procedure will be used to control the type I error and handle multiple endpoints. If the primary endpoint analysis is significant (at the 0.0001 one-sided alpha level at the second interim analysis or at the 0.0249 one-sided alpha level at the final analysis), main secondary efficacy endpoints will be tested sequentially, using the order defined in section "Primary and secondary

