## 11 STATISTICAL CONSIDERATIONS

### 11.1 DETERMINATION OF SAMPLE SIZE

The sample size calculations are based on the primary efficacy variable, with the following assumptions:

- Primary efficacy endpoint is the time from randomization to the date of first occurrence of one of the following Clinical Events, as determined by the CEC: CHD death, any non-fatal MI, fatal and non-fatal ischemic stroke, unstable angina requiring hospitalization. Based on PROVE-IT results (8) and considering adjustment based on the study design and endpoints definition, the following Kaplan-Meier probabilities of event in the placebo group have been considered: 3.8% at 12 months, 6.4% at 24 months, 9.0% at 36 months, 11.4% at 48 months. Probability of event at different time points are estimated using a piece-wise exponential model. The primary efficacy endpoint will be analyzed on an intent-to-treat basis (all randomized patients, including those who discontinue study medication are followed for any efficacy event until the termination of the study)
- Hazard ratio of 0.85 in test group relative to placebo (corresponding to a 15% risk reduction). Constant hazard ratio assumption is used
- A log-rank test at a 1-sided 2.5% significance level with 90% power
- Two interim analyses, according to a group sequential design, using for efficacy Gamma (-22)  $\alpha$ -spending function, and for futility a Gamma (-5)  $\beta$ -spending function. Non-binding spending functions are used. See Section 11.5 for interim analysis details
- 1% lost-to-follow rate at 24 months in both arms
- Enrolment rate: sample size of about 18,600 patients enrolled in 1400 sites (these sites should be active within 12 months). The table below describes the expected enrolment rate per month; these assumptions are based on internal experience to enroll this patient population

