#### **11.4.2.1 Analysis of primary efficacy endpoint(s)**

The analysis of primary efficacy endpoint will be the comparison between the two treatments using the log-rank test procedure stratified by region (North America, South America, Western Europe, Eastern Europe, Asia, Other). As the number of events per individual country is expected to be low (about 50 countries), the analysis will be stratified according to a grouping of countries into regions.

This primary comparison is the test of the following hypotheses on the hazard ratio (HR), applying a one-sided nominal type I error of 0.0249 at the final analysis:

$$H_0: HR \geq 1 \text{ versus } H_1: HR < 1$$

The estimates of the HR and corresponding confidence interval at  $(1-2\alpha)$  % level ( $\alpha$  being the one-sided nominal significance level:  $\alpha=0.249$  at final analysis,  $\alpha=0.0001$  at second interim analysis) will be provided using a Cox Proportional Hazard Model stratified by region as for the log-rank test described above.

Consistency of the treatment effect across regions will be assessed.

Underlying assumptions of the Cox Proportional Hazard Model will be checked using graphical methods. If proportionality is not observed, some ad-hoc sensitivity analyses will be performed depending on the data (data-driven).

The survival curves will be estimated using Kaplan-Meier estimates: cumulative incidence of events at 6 months and by year, and appropriate confidence interval will be presented by treatment arm using Kaplan-Meier estimates. Kaplan-Meier curves will be displayed by treatment arm.

Two interim analyses will be performed See [Section 11.5](#) for description of these analyses. The cut-off dates of final and interim analyses are expected to be:

- First interim analysis (futility): when 807 patients have been experienced at least one primary efficacy event (50% fraction information)
- Second interim analysis (futility and efficacy): when 1210 patients have been experienced at least one primary efficacy event (75% fraction information)
- Final analysis: when 1613 patients have experienced at least one primary efficacy event or 24 months after the last date of randomization ex-China, whichever comes last

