2.2 STATISTICAL MODIFICATIONS MADE IN THE STATISTICAL ANALYSIS PLAN

The statistical analysis plan history table below gives the timing, rationale, and key details for major changes to the statistical analysis features

- in the first version of the statistical analysis plan dated on 25 January 2016 compared to the protocol amendment 8 (version currently in effect at this time)
- in the amended versions of the statistical analysis plan (versions 2 and 3) compared to the first version of 25 January 2016.

Changes already incorporated in a protocol amendment are listed only in Table 2.

With regard to the study timelines, the first patient was enrolled on 02 November 2012. The first interim analysis occurred in April 2016 with the data cut-off for the interim analysis on 30 November 2015. The second interim analysis occurred when approximately 1210 patients had at least one positively-adjudicated primary efficacy endpoint, with review of the data by the DMC in November 2016.

SAP			
version	Date		
number	approved	Rationale	Description of statistical changes
1	25-Jan-2016	Imputation method not planned for missing lipid values	For patients without lipid values in the time window analyzed, multiple imputation will be used with different imputation strategies depending on the time of those missing values (during the treatment period or after treatment discontinuation) (see Section 3.4.7.4.1)
1	25-Jan-2016	End of analysis period for the analysis of TEAEs for patients with 2 consecutives low LDL-C did not take into account down-titrations from 150 mg to 75 mg	In the specific analysis of TEAEs for the subgroup of patients with two consecutive LDL-C <25 mg/dL (respectively 15 mg/dL) within the alirocumab treatment group, the upper limit of the analysis period for patients down-titrated from 150 mg to 75 mg will end at the date of last injection of 150 mg +70 days (see Section 3.4.5.1).
1	25-Jan-2016	Selection of patients with 2 consecutive LDL-C <25 mg/dL (respectively 15 mg/dL) modified consistently with the other studies of the program.	The patients will be considered as having 2 consecutive LDL-C <25 mg/dL (respectively 15 mg/dL) if these values are spaced out by at least 21 days (see Section 3.1.5.4).

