4 INTERIM ANALYSIS

Two interim analyses (IA) are planned, when 50% and 75% of the total number of expected events have occurred:

- Interim analysis for futility will be conducted, when approximately 807 events (50% of the targeted number of primary endpoint events) have occurred;
- Interim analysis for futility and overwhelming efficacy will be conducted, when approximately 1210 events (75% of the targeted number of primary endpoint events) have occurred.

Both IAs will be performed by the external independent CV DMC Statistician and will be reviewed under the supervision of the CV DMC. The CV DMC will also review secondary efficacy endpoints and safety data (adverse events, laboratory data, vital signs) available at the time of the IA.

Control of the type I and type II error will be ensured using gamma (-5) spending function for type II error (futility) and Gamma (-22) for type I error (efficacy) at each IA (the type I error spending function is also applied at the first IA, even if the objective of this first IA is only futility). It has to be noted that, in order to protect the global type I error in case the decision is taken to overrule the futility rule, non-binding boundaries were used.

The following table shows the stopping rules at each interim analysis (using the sample size assumptions described in Section 1.3):

Timing of analyses	Stopping boundaries (1-sided p-value and hazard ratio)	
	Futility	Overwhelming efficacy
First IA: 50% of targeted events	p >0.548 (⇔ HR >1.008)	NA
Second IA: 75% of targeted events	p >0.19 (⇔ HR >0.951)	p <0.0001 ^a (⇔ HR <0.802)

Table 10 - Interim analyses stopping boundaries corresponding to Gamma (-22) type I error and
Gamma (-5) type II error spending functions

HR = hazard ratio; IA = interim analysis; NA = not applicable

a Should the second interim analysis be triggered just before or after 1210 events have been reached, the exact nominal significance level to be used at the second IA would be re-computed based on a Gamma(-22) spending function.

Calculations done using EAST® 5.4

The CV data monitoring committee (DMC) could consider early stopping of the study for overwhelming efficacy at the second IA, if the following conditions are met:

- Stopping boundaries for overwhelming efficacy are crossed;
- Positive trend observed for secondary efficacy endpoints, including all cause mortality, and no excess of non-CV mortality;

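### The second-interim efficacy boundary is printed as HR < 0.802, but Gamma(-22) at 1210 events gives about HR < 0.808; the printed figure is stricter and needs a minor correction

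*Protocol*

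**What the plan says.** Protocol section 11.5 plans a first interim at about 807 events for futility only, and a second at about 1210 events for futility and overwhelming efficacy. Alpha follows Gamma(-22), beta follows Gamma(-5), and the boundaries are non-binding. Protocol Table 4 prints the second-look efficacy boundary as "p < 0.0001* (⇔ HR < 0.802"). SAP Table 10 prints "p <0.0001 ^a (⇔ HR <0.802").

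The Table 4 column header reads "Stopping boundaries (one-sided p-value and Hazard ratio"), so both scales are presented as boundaries, joined by an equivalence sign.

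Other text leans to the p-value. The footnote says that if the look falls just before or after 1210 events, "the exact nominal significance level to be used at the second IA would be re-computed based on a Gamma(-22) spending function". The protocol summary states the criterion for testing the main secondary endpoints only as significance of the primary endpoint "at the 0.0001 one-sided alpha level at the second interim analysis" (or at 0.0249 at the final analysis). Protocol 11.4.2.3 and SAP 3.4.4.3 do the same.

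SAP section 2.2 records that the second interim took place, "with review of the data by the DMC in November 2016".

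**The concern.** A boundary given on two scales should describe one rule. Here the HR does not follow from the spending function named in the table title at the event count named in the same section. An observed HR between 0.802 and about 0.8077 would cross the declared Gamma(-22) boundary and yet miss the printed HR. No sentence says which scale decides if they differ.

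This was the only efficacy look before the final analysis, and boundary crossing is the first of three conditions for the DMC to consider stopping. Anyone who later reports how that look was judged needs to know which number was applied.

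**Working it through.** **Inputs.** Overall alpha is 0.025 one-sided (Protocol 11.1: "A log-rank test at a 1-sided 2.5% significance level with 90% power"). Allocation is 1:1 (Protocol 6). Events are 807, 1210 and 1613 (Protocol 11.4.2.1 and 11.5). Spending is Gamma(-22), and the design HR is 0.85 (Protocol 11.1).

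**Formulas.** Cumulative spend: α(t) = 0.025 × (e^(22t) − 1) / (e^22 − 1). Conversion with 1:1 allocation and D events: HR = exp(−2z/√D). At D = 1210, √D = 34.785.

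**Step 1: check the conversion on the table's futility entries.**
- First look: p = 0.548 gives z = −0.1206, and at 807 events HR = 1.0085 (printed 1.008).
- Second look: p = 0.19 gives z = 0.8779, and at 1210 events HR = 0.9508 (printed 0.951).

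Both agree within rounding. A full group-sequential calculation with Gamma(-5) beta spending also gives 1613.4 events for 90% power (stated 1613), with futility boundaries p = 0.547 / HR 1.008 and p = 0.189 / HR 0.951. The design is therefore being read as intended.

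**Step 2: the efficacy boundary under Gamma(-22).**
- α(0.75) = 0.025 × (e^16.5 − 1)/(e^22 − 1) = 0.0001022, so z = 3.7136.
- HR = exp(−2 × 3.7136/34.785) = 0.8077.
- Recursive integration with t = 1210/1613, allowing for the first-look spend of 4.2 × 10⁻⁷, gives z = 3.7130, p = 0.0001024, HR = 0.8078.

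**Step 3: what the printed figures correspond to at 1210 events.**

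| Boundary | z | one-sided p |
|---|---|---|
| Gamma(-22): HR 0.8077 | 3.714 | 0.000102 |
| p exactly 0.0001: HR 0.8075 | 3.719 | 0.000100 |
| Printed HR 0.802 | 3.838 | 0.000062 |

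A p of 0.000062 prints as 0.0001 at four decimals, so the printed p and HR could agree by rounding. The firm conflict is between HR 0.802 and Gamma(-22).

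**Step 4: other explanations.**
- *Event count.* Gamma(-22) reaches HR 0.802 at about 1185 events (1185/1613 = 73.5%), whereas the row is stated for 75%.
- *Two-sided reading.* p = 0.00005 gives HR 0.7996.
- *Freedman conversion.* HR 0.8071.
- *Unequal event split under HR 0.85.* HR 0.8072.
- *Different parameter.* Gamma(-24) gives p = 0.0000622 and HR 0.8020. This matches, but neither document names Gamma(-24).

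**Step 5: consequences.** The mean of z at 1210 events is −ln(HR) × 34.785/2, which is 2.827 for a true HR of 0.85 and 3.881 for 0.80. The chance of crossing is the upper normal tail beyond the boundary z minus that mean.

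| True HR | Gamma(-22) | p = 0.0001 | Printed HR 0.802 |
|---|---|---|---|
| 0.85 | 18.8% | 18.6% | 15.6% |
| 0.80 | 56.6% | 56.4% | 51.7% |

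The scales therefore disagree with probability 3.0% to 3.2% at a true HR of 0.85, and 4.7% to 4.9% at 0.80. Under the null, the alpha at this look falls from 0.000102 to 0.000062, about 0.00004 of the 0.025. The final nominal level is 0.0250 to four decimals with either interim boundary.

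**The case against.** The mismatch itself is not disputed. Four objections remain.

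**The source of the slip is unknown.** Gamma(-24) reproduces 0.802, and changing the alpha parameter from -22 to -24 leaves the futility boundaries, the required events and the final level unchanged to the printed digits. The table cannot show whether 0.802 is a typing error or output from a run with another parameter. This stands, and it is why the EAST output should be checked first. It does not rescue the figure: the table titles, the footnote and every statement of the rule name Gamma(-22).

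**The p-value already governs in practice.** The footnote recomputes only the significance level, the testing rules use only the p-value, and the primary test is a stratified log-rank test with the Cox model supplying the HR estimate. This largely stands and limits the consequence. The disagreement probabilities matter only if someone applied the HR. Still, the header lists both scales as boundaries, and nothing states the precedence.

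**The equivalence was always approximate.** The observed HR comes from a stratified Cox model and the p-value from a log-rank test. That is true, but the futility cells agree to about 0.001 in HR, while this one is off by nearly 0.006.

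**The look is over.** A later edit to the cell cannot change a decision and could obscure what the DMC saw. This is a fair reason to record the correction openly with a dated note.

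**Conclusion.** The concern holds, at minor severity. Against the declared Gamma(-22) rule at 1210 events, the efficacy HR should be about 0.8077, and the printed 0.802 is too strict by nearly 0.006. The error is conservative. Type I error is protected, the stated final level of 0.0249 remains valid, and the cost is about 3 percentage points of crossing probability at the design HR, and only if the HR scale was used. Crossing alone never sufficed: the plan also requires supportive secondary endpoints including all-cause mortality, no excess of non-cardiovascular mortality, and consistency across subgroups and regions.

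The result rests on 1:1 allocation, the standard log-rank approximation for converting z to HR, and the look falling at 1210 events. The actual event count is given only as approximately 1210. Confidence is high that 0.802 does not match Gamma(-22). That the HR, and not the gamma parameter, is the slip is an inference from the consistent naming of Gamma(-22).

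**What to change.** 1. Check the EAST 5.4 output to confirm that the boundary was run with Gamma(-22).
2. If so, replace HR < 0.802 with HR < 0.807 in Protocol Table 4 and SAP Table 10. Rounding down keeps the HR inside the p-value boundary: HR 0.807 at 1210 events is z = 3.7295, p = 0.000096, whereas HR 0.808 would be p = 0.000104, just outside.
3. Add one sentence to both documents: the boundary is the nominal one-sided p-value from Gamma(-22) at the actual event count, and the HR is its approximate translation at 1210 events.
4. Because the look was reviewed in November 2016, record in a dated note the actual event count, the boundary shown to the DMC and the scale applied.

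A separate clerical slip can be corrected at the same time. Protocol 11.4.2.1 gives the final-analysis alpha for the confidence interval as 0.249. Read literally, that is a 50.2% interval (1 − 2 × 0.249 = 0.502). The same section and SAP 3.4.4.1 give 0.0249, which is the value to print. This slip carries no weight in the point above.

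The cost is one cell in two tables, one added sentence, a short note on the completed look and one decimal. The final analysis and trial operations do not change.
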